### **Rationale for Selecting Sleep Duration as a Personalized Trial**

Sleep is an important and complex physiological process for maintaining optimal health. The National Sleep Foundation recommends  $\geq 7$ h of sleep per night on a regular basis for adults aged 18-60 years. During the first two COVID-19 pandemic waves, findings indicated a high prevalence of both poor sleep quality and moderate-severe stress in healthcare workers (HCWs) (either at the frontline or not), and especially amongst women. Studies conducted in a cohort of New York City HCWs (80% women,  $>50\%$  nurses, median age of 36 years) showed that during the pandemic, the rates of insomnia symptoms (e.g., short duration, poor quality sleep) were approximately 20% higher than rates reported in 2018, and revealed an association between poor sleep quality and a higher prevalence of psychological distress. Thus, evidence suggests that sleep may be a target intervention to decrease psychological distress among HCWs. While some mitigation interventions (e.g., reducing workload) have been proposed to address stress/burnout on HCWs very few have focused on women in healthcare and specifically targeted sleep as a symptom of stress. The primary goal of this pilot study is to determine if a personalized trial (N-of-1) employing a Mind-Body Intervention (MBI) can produce a meaningful increase in sleep duration among women 40-60 years of age and older working at Northwell Health. N-of-1 studies are single-patient crossover trials, where individual patients are given candidate treatments in a random sequence of alternating periods to determine the most effective treatment for that patient. In contrast to randomized controlled trials, which provide evidence on a population level, N-of-1 trials provide a method to determine what works best for the individual directly. Up to 65 women with a history of short sleep duration (defined as an average  $<7$ h per 24-h period for at least three months) will be enrolled (randomized) over a period of two years. Participants will complete a 2-week run-in period with no intervention, for baseline data collection, including bi-weekly surveys and Fitbit-derived sleep and activity data. Those who are deemed eligible and achieve at least 80% adherence of Fitbit wear and survey submission will be randomized to Arm 1 (N=30) or Arm 2 (N=30). Each arm will receive a personalized intervention comprised of three components: mindfulness, yoga and guided walking assigned in 2-week block sequences for a total period of 12 weeks. Following the intervention, all participants will be assessed over a 2-week follow-up period. Changes in average daily sleep duration will be calculated for each participant based on daily measurements between the run-in and each treatment period. The Fitbit devices will also record sleep quality components (sleep onset, sleep staging, and overall sleep score) and physiological factors (resting heart rate, heart rate variability (HRV) and activity). **We will also examine the direct and indirect relationships between perceived stress, anxiety and depression, and sleep quality assessed pre, during (bi-weekly), and post MBI.**

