## 8. NUMBER OF SUBJECTS

- *Indicate the total number of subjects to be accrued locally. If applicable, distinguish between the number of subjects who are expected to be pre-screened, enrolled (consent obtained), randomized and complete the research procedures.*
- *If your study includes different cohorts, include the total number of subjects in each cohort.*
- *If this is multisite study, include total number of subjects across all sites.*

Up to 1000 potential participants may be screened for study eligibility. Up to 65 participants will be randomized until 60 (30 participants in each arm) complete research procedures with any data (Fitbit or survey) post- randomization. Eligible participants will be randomized (1:1) into Arm 1 or Arm 2. In Arm 1 (N=30), participants will receive a personalized intervention comprised of three components delivered in a ABCCBA sequence over a total period of 12 weeks, where A- mindfulness, B-yoga, and C-guided walking. During each 2-weeks block, participants will be prompted to complete 3 x 30-minute intervention sessions weekly. In Arm 2 (N=30), participants will receive a personalized intervention comprised of the same three components delivered in a CBAABC sequence over a total period of 12 weeks. Prompts will be delivered weekly to Arm 2 as well.

[figure not shown]

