### **Sample size justification:**

The primary aim of this study is to evaluate the effect of a personalized MBI on increasing the average daily sleep duration in working at Northwell Health. A sample size of 30 participants per arm achieve 80% power to detect a minimum effect size of 0.7 expected by one of the three Aim 2 interventions. Calculations were based on GEE tests for repeated measures considering a total of 28 daily measurements (4 weeks) per intervention, at a significance level of 0.05. The within subject standard deviation  $\sigma$  is anticipated to be maximum 2h, with an auto-regressive AR(1) base correlation of 0.95 taken at two successive timepoints. Estimated effect size and correlation values were derived from a previous fatigue study that employed similar intervention/design and collected sleep duration as exploratory endpoint.

The **randomization schedule** will be set up by a member of the Institute of Health System Science data team and provided to the data analyst assigned to this trial.. Randomization will occur with a fixed seed value for the purposes of repeatability and auditability, and the list of participants will be split into two groups using a

random shuffle function that takes that seed as input. The order in which an individual becomes eligible for one of these randomizations will determine the placement given (i.e. the first person eligible will be randomized to the intervention order given to participant 1 and continue sequentially). Eligibility is obtained by a participant maintaining at least 80% adherence of survey response, Fitbit wear  $\geq 12$  hours a day 80% of days, and 80% sleep data  $\geq 180$  minutes available through the baseline run-in period. The data analyst will alert the research coordinator of the assigned randomization once a participant becomes eligible during the baseline run-in period. As this pilot is not blinded to study coordinators, this concealed allocation involving the data analyst alerting the study coordinator of intervention assignment will be used to prevent bias by blinding the sequence up until time of randomization.

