### **Analytical Plan**

**Primary Outcome** – Mean Within-Subject Difference in daily sleep duration during 3 treatment periods from baseline. Participant's sleep duration will be measured objectively using Fitbit devices and by self-reported questionnaires. The Fitbit devices will collect information continuously that will be stored in Fitabase, a secure, online portal. Participant sleep activity will be aggregated by day.

Analysis of Primary Outcome: The effect of the personalized MBI intervention on individual's sleep duration will be assessed in each arm separately. Individual changes in the average daily sleep durations between the run-in and each treatment period will be reported using mean (95% confidence intervals CIs). Bland-Altman plots will be constructed to visualize the agreement between the Fitbit reported and self-reported sleep duration. The effects of treatment on sleep duration will be assessed using generalized estimating equations (GEE) with an unstructured variance-covariance matrix for measures on the same day to that night's sleep. This model accounts for possible autocorrelation and linear trends between sleep duration across time. The GEE models will include time of day of treatment exposure (AM versus PM) as a covariate.

**Exploratory Aim 1 Outcomes** - Mean Within-Subject Difference in daily sleep quality and other physiological factors during 3 treatment periods from baseline. This aim will explore the effects of the personalized intervention on sleep quality components (sleep onset, sleep staging, and overall sleep score) and physiological factors (breathing/resting heart rate, heart rate variability (HRV) and physical activity). All these measurements will be recorded and aggregated daily by the Fitbit device.

Analysis of Exploratory Aim 1 Outcome: The effect of the personalized MBI intervention on individual's sleep quality and physiological factors will be assessed in each arm separately. Individual changes in the average daily sleep quality (e.g., score), heart rate and daily average number of steps between the run-in and each treatment period will be reported using means (95% CIs. GEE models will be employed to test the effect of the intervention of sleep quality and physiological factors.

**Exploratory Aim 2 Outcomes** – Mean Within-Subject Difference in perceived stress, anxiety and depression scores measured objectively during 3 treatment

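### The sleep effect is to be assessed arm by arm, and the plan does not say whether the GEE combines two arms that differ only in component order

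*Combined protocol and SAP*

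**What the plan says.** Section 12, Analytical Plan, opens the analysis of the primary outcome by saying that the effect on "sleep duration will be assessed in each arm separately". It goes on: "Individual changes in the average daily sleep durations between the run-in and each treatment period will be reported using mean", with 95% confidence intervals. Section 3 describes the same quantity: "Changes in average daily sleep duration will be calculated for each participant based on daily measurements between the run-in and each treatment period".

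After a sentence on Bland-Altman plots comes the GEE, with an unstructured matrix. Of this model the plan says: "This model accounts for possible autocorrelation and linear trends between sleep duration across time". The only covariate named is AM versus PM exposure. No sequence term is named, and nothing says whether one model covers both arms. Exploratory Aim 1 repeats the wording: "sleep quality and physiological factors will be assessed in each arm separately".

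Section 8 defines the arms, randomised 1:1. Arm 1 receives an intervention "comprised of three components delivered in a ABCCBA sequence over a total period of 12 weeks" (A mindfulness, B yoga, C guided walking). Arm 2 receives one "comprised of the same three components delivered in a CBAABC sequence over a total period of 12 weeks". Section 19 mentions pooling of N-of-1 data as a general benefit, without reference to the arms or the GEE.

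**The concern.** The two arms are not two treatments. They are two orders of one crossover, and the reversed order helps a component comparison only if the arms are analysed together.

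As written, two analysts could reasonably fit different primary models: one GEE on about 60 participants, or two GEEs on about 30 each. Under the second reading the primary outcome has two estimates per component, no rule for combining them, and wider intervals. A group-level comparison of walking with mindfulness would also be exposed to any time course that is not a straight line, because these two components swap positions between the arms.

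**Working it through.** **1. The plan's own figure.** Section 12 states 30 per arm for 80% power at effect size 0.7, alpha 0.05 and 28 daily measures, where the SD "is anticipated to be maximum 2h, with an auto-regressive AR(1) base correlation of 0.95". With n per arm = 2v(z₀.₉₇₅ + z₀.₈₀)²/d², where v is the variance of a 28-day mean relative to one day:

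- Day-to-day AR(1) 0.95 gives v = 0.654. With d = 0.7 SD, n = 2 × 0.654 × 7.85/0.49 = 21, and power at 30 is 91.8%.
- Constant correlation 0.95 gives v = (1 + 27 × 0.95)/28 = 0.952, so n = 30.5, and power at 30 is 79.4%.
- If 0.7 means hours, d = 0.7/2 = 0.35. With v = 0.654, n = 84.

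The unit of 0.7, the sidedness and the contrast are not stated, so 30 is neither confirmed nor refuted. Nothing below depends on it.

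**2. Balance within one arm.** Mindfulness is in blocks 1 and 6 in Arm 1 and blocks 3 and 4 in Arm 2. Walking is the reverse. Yoga is in blocks 2 and 5 in both. Every component has mean position 3.5, so linear drift cancels within an arm. Squared distance from mid-trial is 2.5² = 6.25, 1.5² = 2.25 and 0.5² = 0.25 for the three positions. On block means, a quadratic is therefore indistinguishable from component differences within one arm.

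**3. Precision.** With unweighted means and 60 participants instead of 30, the ratio of standard errors is √(60/30) = 1.41 at any correlation. The table uses generalised least squares on daily data: 14 run-in and 84 treatment days, 30 per arm, SD 2 h, linear trend, no missing days, and a sequence term when pooled.

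| Contrast | AR(1) | Per arm (h) | Pooled (h) | Ratio |
|---|---|---|---|---|
| Average intervention minus run-in | 0.95 | 0.129 | 0.083 | 1.6 |
| Average intervention minus run-in | 0.5 | 0.202 | 0.143 | 1.4 |
| Walking minus mindfulness | 0.95 | 0.114 | 0.073 | 1.6 |
| Walking minus mindfulness | 0.5 | 0.155 | 0.109 | 1.4 |

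Only the SD and the 0.95 come from the plan; 0.5 is an assumption added to show a range.

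**4. Order artefact.** Assume no component difference and the same time course in everyone. Take a course of 0, 20, 30, 30, 30, 30 min over the six blocks. In Arm 1 the raw changes are mindfulness (0 + 30)/2 = 15, yoga (20 + 30)/2 = 25 and walking (30 + 30)/2 = 30. In Arm 2 mindfulness and walking exchange values. Walking minus mindfulness is +15 and −15, and the average is 0.

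The smooth course below is 30(1 − exp(−t/14 days)) from the start of treatment. Entries are walking minus mindfulness in Arm 1, in minutes. Arm 2 is the negative, and pooled is 0.

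| Course and per-arm model | AR(1) 0.95 | AR(1) 0.5 |
|---|---|---|
| Stepped, linear trend | 14.9 | 14.9 |
| Stepped, quadratic | 15.2 | 16.3 |
| Smooth, linear trend | 1.1 | 7.3 |
| Smooth, quadratic | 0.2 | 1.9 |
| Linear drift, linear trend | 0 | 0 |

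At correlation 0.5 the per-arm quadratic raises the standard error of this contrast from 0.155 to 0.262 h.

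**5. What pooling leaves.** In the stepped illustration the pooled raw changes from run-in are (15 + 30)/2 = 22.5 min for mindfulness and walking and 25 min for yoga. The change from run-in still contains the whole time course, and yoga still differs from the others by 2.5 min.

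**The case against.** The strongest reply is that the GEE sentence carries no restriction by arm. The arm-by-arm phrase sits next to the descriptive mean changes and may apply only to them, and Section 19 speaks of pooling. That stands: the plan is silent on pooling in the GEE and does not exclude it. A reader might infer that the primary outcome will certainly be reported twice. The documents do not support that, so the consequences here are conditional on a per-arm fit. The ambiguity remains, because the phrase governs the effect itself and opens the primary analysis.

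Second, the order bias falls on a contrast that is not the primary outcome. The Primary Aim concerns increase from baseline, and Section 4 asks which component works best for each individual; no group-level walking-against-mindfulness test is specified. This also stands, and it is why precision and the missing combination rule come first. A reader might infer that pooling frees the primary result from time effects. It does not, because run-in always comes first.

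Third, the 15 min figure comes from jumps placed exactly at block boundaries, which mimic a component effect. At the plan's own 0.95, a smooth rise gives 1.1 min, and a per-arm quadratic nearly removes it. No document supports any particular curve, so the range matters more than its top.

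Fourth, the standard errors assume AR(1) weighting, whereas the plan names an unstructured matrix. They are illustrative; the 1.41 ratio for simple means does not need that assumption.

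**Conclusion.** The point holds as an ambiguity that should be resolved before analysis. If the GEE is fitted per arm, the change from run-in is estimated twice without a combining rule, and intervals are about 1.4 times as wide as pooled (1.4 to 1.6 under AR(1) weighting with a linear trend). The order artefact in walking minus mindfulness is secondary. It ranges from zero (linear drift) through 0.2 to 7.3 min (smooth rise, depending on correlation and time model) to about 15 min (stepped course).

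These sizes assume SD 2 h, 30 complete participants per arm and a time course common to both arms. It would be tempting to conclude that the trial is underpowered. The documents do not support that: the sample size is stated per arm, the contrast it powers is undefined, and wider intervals than a pooled analysis do not show the stated 80% to be wrong.

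**What to change.** In Section 12, Analysis of Primary Outcome, state that the primary GEE is fitted to all randomised participants from both sequences, with terms for component, sequence and pre-specified time (for example linear, with a quadratic as sensitivity analysis) plus the AM/PM covariate already planned. Label by-arm results as descriptive. Use the same wording for Exploratory Aim 1.

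State the limits beside it:

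- Changes from run-in remain confounded with time.
- Yoga contrasts still depend on the time model, because yoga occupies blocks 2 and 5 in both arms.
- Individual reports keep the order limit, since each participant follows one sequence.
- Pooling assumes that a component's effect is the same in either order; the by-arm results let readers check this.
- Cancellation is exact only with equal weight per sequence. With 35 and 30 participants, a plain average in the stepped illustration leaves 15 × 5/65 = 1.2 min.

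The cost is wording only; arms, sequences, sessions and sample size do not change. In the pooled model a quadratic leaves the walking-minus-mindfulness standard error at 0.073 h (AR(1) 0.95) or 0.109 h (0.5). It raises that of mindfulness or walking minus run-in from 0.090 to 0.091 h, or from 0.154 to 0.193 h.

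### The primary GEE rests on about 30 participants per arm, yet the plan names no variance estimator, reference distribution or small-sample correction; usual defaults would run somewhat above the 0.05 level

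*Combined protocol and SAP*

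**What the plan says.** All of this is in section 12 (Statistical Analysis) of the combined protocol and SAP, except the allocation.

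- **Model.** Under Analytical Plan, the effects of treatment on sleep duration are to be "assessed using generalized estimating equations (GEE) with an unstructured variance-covariance matrix". The text adds that the model allows for autocorrelation and linear trends, and it includes a morning-versus-afternoon exposure covariate. GEE models are also named for Exploratory Aim 1.
- **By arm.** The paragraph on the primary outcome opens by saying that the effect on "sleep duration will be assessed in each arm separately". The later GEE sentence does not repeat this and does not say that the arms are pooled.
- **Level and size.** The sample size paragraph bases its calculation on GEE tests "at a significance level of 0.05" and states: "A sample size of 30 participants per arm achieve 80% power to detect a minimum effect size of 0.7". Section 8 adds: "Eligible participants will be randomized (1:1) into Arm 1 or Arm 2", with 30 in each.
- **Silence.** Nothing in section 12 names a robust, empirical or model-based variance, a normal, chi-square, t or F reference, or a small-sample adjustment.

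**The concern.** In a GEE the independent units are participants, not nights. Fourteen weeks of daily data do not turn 30 people into a large sample. The sandwich variance is justified when the number of independent units is large. At about 30 it tends to be too small, for two reasons: residuals from a fitted model understate the true variation, and a normal critical value ignores the uncertainty in the variance estimate. Both push p-values down.

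An unstructured working matrix makes this worse, because many extra parameters are estimated from the same 30 people. The plan asks for that matrix without saying how many time points it covers.

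At stake is whether the 0.05 level on which the sample size rests is the level at which the primary tests would actually run.

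**Working it through.** **1. The plan's own sample size figure.** Stated inputs: 30 per arm, 80% power, effect 0.7, level 0.05, SD that "is anticipated to be maximum 2h", AR(1) with a "base correlation of 0.95 taken at two successive timepoints", and a calculation "considering a total of 28 daily measurements (4 weeks) per intervention".

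- Under AR(1) with 0.95, the variance of a 28-day mean is 0.654 of the daily variance.
- Two groups, two-sided, 0.7 in SD units: n = 2 × (1.960 + 0.842)² × 0.654 / 0.7² = 20.95, so 21 per arm (power at 30 is 91.8%).
- Ignoring the repeated measures: 2 × (1.960 + 0.842)² / 0.7² = 32.04, so 33 per arm (power at 30 is 77.4%).
- Reading 0.7 as hours over a 2 h SD (0.35): 84 per arm.

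The stated 30 per arm at 80% does not follow from the stated inputs without further unstated choices. Sidedness, the unit of the effect and the comparison tested are not given. This does not affect the present point, which needs only the number of participants and the level.

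**2. Simplest case, in closed form.** Assumptions: one mean change per participant, normal and complete data, two-sided 5%. The uncorrected sandwich divides by n instead of n − 1 and is compared with 1.96.

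- True size = P(|t with n − 1 df| > 1.96 × √((n − 1)/n)).
- n = 30: threshold 1.96 × √(29/30) = 1.927, size **6.4%**.
- n = 60: threshold 1.96 × √(59/60) = 1.944, size **5.7%**.
- Width of a correct interval relative to the default at n = 30: 2.045 × √(30/29) / 1.96 = **1.06**.

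**3. Simulation of the design under no effect.** 10,000 runs; 98 days (14 run-in plus 84 intervention); component indicators; with and without the linear trend and the AM/PM term. The assumptions not taken from the plan are normal data, complete follow-up and the AM/PM patterns.

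| Setting | Method | Error rate per component |
|---|---|---|
| 30 people, independence or AR(1) working matrix | uncorrected, normal reference | 6.1% to 6.9% |
| same | uncorrected, t reference | 5.0% to 5.5% |
| same | Kauermann-Carroll, t reference | 4.6% to 5.2% |
| same | Mancl-DeRouen, t reference | 4.2% to 4.8% |
| 30 people, unstructured matrix on seven two-week means | uncorrected, normal reference | 8.3% to 9.9% |
| same | uncorrected, t reference | 6.8% to 8.4% |
| 60 people, independence working matrix | uncorrected, normal reference | 5.4% to 5.5% |

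With the simple working matrices, the default standard errors averaged 0.96 to 0.98 of the true value at 30 people. With the unstructured matrix on seven means they averaged 0.86 to 0.91. The corrected variances were tested only with the simple working matrices. The run with 60 people gave everyone the Arm 1 sequence.

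**4. The matrix itself.** Read literally over 98 days, an unstructured matrix has 98 × 97 / 2 = 4,753 correlations. Its moment estimate from 30 people has rank at most 30, so it cannot be inverted as a working matrix. Pooling 60 people would not change that, since 60 is still below 98. On seven period means it has 7 × 6 / 2 = 21 correlations and can be fitted, at the cost shown in the table.

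**5. Joint test of three components, if one were made.** True size = P(F with 3 and n − 3 df > 7.815 × (n − 3)/(3n)). At n = 30 the threshold is 7.815 × 27/90 = 2.34 and the size is 9.5%.

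**The case against.** **The plan never says it will use ordinary robust errors.** This stands. A reader might infer that the 0.05 level will not be held. The documents do not support that, because the estimator and reference are left open. What they support is that these choices are unspecified and that the usual default would exceed the level.

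**The by-arm reading is not explicit for the GEE.** This stands in part. The by-arm sentence opens the same paragraph, so it is the natural reading. The GEE sentence itself is silent, and section 19 speaks of pooling the individual trial data. Pooled over 60 with a simple matrix, the excess is negligible for a single component.

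**The 95% confidence intervals in the plan are not GEE intervals.** This stands. They are attached to individual changes from run-in to each treatment period, in a separate sentence. It would be wrong to say that those intervals are too narrow for the reason given here; the 6% figure concerns only GEE-based intervals, if any are reported.

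**No joint test is planned.** This stands. The power statement refers to one of the three interventions. The 9.5% figure is a warning for any such test, not a measure of a planned one.

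**Thirty per arm may not be the evaluable number.** Section 8 counts people with any post-randomization data, so a reader might infer fewer usable participants and greater inflation, for example with 24 per arm. The documents give no such number; 24 would be an assumption.

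**The excess is small and this is a pilot.** This stands for a simple working matrix, where it is one to two percentage points. It does not stand for the unstructured matrix that the plan names. The plan also claims 80% power at 0.05, and section 23 says the data are to support larger trials.

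**Conclusion.** The point holds in conditional form. Fitted by arm on about 30 participants with the usual default, the primary GEE would have a true error rate of about 6% to 7% per component under a simple working matrix, and about 8% to 10% under an unstructured matrix on seven period means. Pooled over 60 with a simple matrix it would be about 5.5%.

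This rests on by-arm fitting, two-sided tests, normal and complete data, and an uncorrected sandwich with a normal reference. None of these is stated outright in the plan. Confidence is medium. This is a cheap improvement rather than a flaw that undermines the trial. The larger share of the possible inflation comes from the unstructured matrix, so the working correlation and the variance estimator should be settled together.

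**What to change.** Add to the Analytical Plan, for the primary and Exploratory Aim 1 GEE models:

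- whether each model is fitted by arm or pooled;
- a parsimonious working correlation, such as AR(1), in place of the unstructured matrix;
- a small-sample-corrected sandwich variance, for example Kauermann-Carroll or Mancl-DeRouen;
- t or F reference distributions with degrees of freedom based on participants, not nights. This applies equally to any joint test of the three components.

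The minimum is a t reference alone. That is enough with a simple working matrix, but not if the unstructured matrix is kept.

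The cost is a sentence or two in the plan and a software option. Any GEE-based intervals become about 6% wider and p-values slightly larger. In the simulations Mancl-DeRouen was a little conservative (4.2% to 4.8%), and Kauermann-Carroll was closer to 5%.

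### The primary GEE names an unstructured matrix without tying it to a cluster or repeated unit; on the nightly reading (98 nights, about 30 participants per arm) that matrix cannot be validly estimated

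*Combined protocol and SAP*

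**What the plan says.** All of the model wording is in Section 12, Analytical Plan.

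- **Outcome.** The primary outcome is the average change within a participant, from baseline to the treatment periods. On measurement: "sleep duration will be measured objectively using Fitbit devices and by self-reported questionnaires". On the level of the record: "Participant sleep activity will be aggregated by day".
- **Analysis set.** The effect on "sleep duration will be assessed in each arm separately".
- **Descriptive part.** "Individual changes in the average daily sleep durations between the run-in and each treatment period will be reported using mean", with 95% confidence intervals.
- **Test of treatment effect.** "generalized estimating equations (GEE) with an unstructured variance-covariance matrix for measures on the same day to that night's sleep". The next sentence adds: "This model accounts for possible autocorrelation and linear trends between sleep duration across time". The only covariate listed is whether the exposure was in the morning or the evening.
- **Exploratory Aim 1.** "GEE models will be employed to test the effect of the intervention of sleep quality and physiological factors", with no correlation structure named.

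The only explicit between-night structure is in the sample size justification, which plans on 28 daily values per component "with an auto-regressive AR(1) base correlation of 0.95 taken at two successive timepoints". The analysis paragraph does not refer back to it.

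**The concern.** A GEE needs three statements before it can be programmed: what the cluster is, which repeated measures index the working matrix, and what form that matrix takes. The plan gives only the third, and the qualifying clause about same-day measures leaves unclear what its rows and columns are.

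This matters because the most natural reading cannot be carried out. If the rows are nights, far more correlations have to be estimated than 30 participants can support. The structure would then be settled after the data are seen, or by whatever the software does with a matrix it cannot invert. The model concerned is the only one named for testing the treatment effect on the primary outcome.

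**Working it through.** The plan gives no figure for the size of the matrix, so there is none to reproduce. One planning figure helps with the reading: 28 daily measurements per component equals 2 blocks x 14 days, which is one value per day.

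**Inputs**
- Run-in: 2 weeks = 14 nights (Section 9).
- Intervention: six 2-week blocks = 84 nights (Section 11).
- Participants: 30 per arm, up to 65 randomized (Section 8); arms analysed separately (Section 12).
- SD at most 2 h, AR(1) 0.95 (sample size justification).
- Assumed for the simulations: normal data; complete nights unless stated; arm 1 order ABCCBA; a mean model with an intercept and one term per component. The AM/PM covariate is left out.

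**1. Size of the matrix.** T = 14 + 84 = 98. Correlations = T(T - 1)/2 = 98 x 97/2 = 4,753. For comparison, seven period means need 7 x 6/2 = 21, AR(1) needs 1 and independence needs none.

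**2. Can it be estimated?** The moment estimate is S = (1/n) x sum of e_i e_i', a sum of n rank-one terms, so its rank is at most n.
- One arm: rank 30 of 98. Both arms pooled: 60 to 65 of 98. Simulation gives exactly these ranks.
- Fixing the diagonal at 1 restores full rank but makes the matrix indefinite: about 26 to 45 negative eigenvalues at n = 30, and about 23 to 40 at n = 60 to 65.
- With 20% of nights missing at random (assumed), the count at n = 30 is about 43 to 57.

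Robust standard errors do not cure this, because the working matrix must be inverted to obtain the estimate itself.

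**3. One possible repair.** A generalised inverse was forced in 400 null datasets under AR(1) 0.95. In 64 there was no usable fit, and 12.8% of the other 336 rejected at nominal 5%. Under a weaker assumed correlation 9.0% rejected. Another repair would give other figures.

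**4. The other readings**
- *Measures within one day* (for example Fitbit and diary, 2x2): estimable, but the matrix then says nothing about correlation between nights.
- *Seven period means* (7x7, 21 correlations): estimable, but not stated. Null rejection is 9.3% with ordinary robust errors and 6.5% after a small-sample correction.

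**5. Independence working correlation, participant as cluster.** On complete data the mindfulness estimate in arm 1 is the mean of its 28 nights minus the mean of the 14 run-in nights. Let c hold weights 1/28 on the former and -1/14 on the latter, and let R have entries 0.95^|j-k|. Then sqrt(c'Rc) = 0.831, and SE = 2 x 0.831/sqrt(30) = 0.303 h. Null rejection is about 6.4% with ordinary robust errors, and about 4.6% with the Mancl-DeRouen correction and t on 26 degrees of freedom. A paired t-test on period means gives 4.5%.

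**6. AR(1) working correlation.** The SE falls to about 0.11 h, but the target can change. The expected estimate is (X'WX)^-1 X'W mu, with W the inverse of R. Let the true period-mean effect be 1 h for mindfulness and 0 for yoga and walking. The onset patterns are assumed, each scaled to a block mean of 1 h.

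| Pattern within a block | AR(1) 0.95 weights (mindfulness, yoga, walking) | Independence weights |
|---|---|---|
| Full from night 1, stops at once | 1, 0, 0 | 1, 0, 0 |
| Builds in equal steps, full by night 4 | 0.32, -0.39, -0.39 | 1, 0, 0 |
| 0.5 h in week 1, 1.5 h in week 2 | 0.54, -0.46, -0.46 | 1, 0, 0 |

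AR(1) 0.95 relies mainly on the jump from one night to the next at a block change. It therefore matches the stated period-mean outcome only when effects start in full and stop at once.

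**The case against.** The strongest reply is that the text is not silent on the unit. Sleep is summarised by day, the sample size counts daily values, and the outcome is a within-participant change. The word unstructured is also limited to same-day measures, so a 98x98 matrix may never have been meant. The individual changes with confidence intervals can be produced whatever happens to the GEE, and this is a minimal-risk pilot.

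Much of this stands. The gap is that the matrix is not tied to the daily unit, not that no daily unit exists. The individual summaries are unaffected. But if the clause covers only same-day measures, this matrix does not model the autocorrelation that the model is said to handle, so a sentence is still needed. Pilot status does not remove the point: Section 4 speaks of fully powered pilots, and the sample size rests on a GEE test at 0.05.

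A reader might infer more than the documents support:

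- *That the day is the cluster, so the test would be badly anti-conservative.* Nothing names the day as cluster, the outcome points to the participant, and the effect on the error rate would depend heavily on the assumed correlation.
- *That the ambiguity moves the standard error nearly threefold.* That sets 0.30 h against 0.11 h, but the latter belongs to AR(1), which the analysis paragraph does not name. The two estimable unstructured readings, with the participant as cluster, give 0.296 h and 0.254 h, a ratio of 1.17.
- *That naming the participant as cluster is enough.* The 7x7 result of 9.3% shows that a small-sample correction is needed too.
- *That AR(1), being in the sample size section, should simply be carried over.* Step 6 of the working shows why it can miss the stated outcome. The plan describes consecutive 2-week blocks with three sessions a week and gives no evidence of immediate onset and offset.

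**Conclusion.** The point holds and should be fixed. The test of the primary outcome cannot be programmed from the plan as written. On the best-supported reading the named matrix is singular or indefinite, with rank 30 of 98 per arm and at most 65 of 98 pooled. The rank result is algebra and needs no distributional assumption. It rests on the nightly reading and on about 30 participants per arm.

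The documents do not support saying that the trial's error rate is inflated by a known amount. That depends on a repair the plan does not name, and other readings of the clause can be estimated. The simulated error rates rest on normal data, the planning correlation and a model without the AM/PM covariate. The design and the individual summaries are not in question.

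**What to change.** In Section 12, Analysis of Primary Outcome:

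- State that the GEE is fitted to nightly values with the participant as the cluster.
- Replace the unstructured matrix with an independence working correlation. Clustering the robust variance by participant then carries the between-night correlation, and on complete data the component terms remain the stated period-mean differences.
- Use participant-clustered robust standard errors with a small-sample correction (for example Mancl-DeRouen) and a t reference.
- Do not make AR(1) the primary working structure.
- Because linear trends are said to be accounted for, list the time term (day or 2-week block) in the mean model.
- Use the same specification for the Exploratory Aim 1 GEEs.

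Analysing period means with the participant as the unit, for example by paired t-test, is an equivalent alternative if the sponsor prefers it.

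**Cost.** A few sentences, with no new data or participants. Three downsides should be accepted openly:

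- **Precision.** Under AR(1) 0.95 the standard error for mindfulness against run-in is about 0.30 h, against about 0.11 h with AR(1) weights. The smaller figure is valid only under immediate onset and offset.
- **Time term.** Run-in always comes first, so a time term widens the intervals against run-in. Adding a linear day column to X in SE^2 = the mindfulness diagonal element of (X'X)^-1 X'VX (X'X)^-1 / 30, with V = 4R, raises 0.303 h to 0.337 h, about 11%. The component terms then become trend-adjusted differences.
- **Missing nights.** With unequal numbers of nights, independence weights give more weight to participants who contribute more nights, so the match with simple period means is no longer exact.
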